TMS is a noninvasive method to cause depolarization or hyperpolarization in the neurons in the brain using electromagnetic induction to induce weak electric currents using a rapidly changing magnetic field. TMS is a novel intervention developed in the field of neurology that has been used in the treatment of patients suffering from migraine, stroke, Parkinson's disease, tinnitus and depression. In healthy subjects, high frequency rTMS over the left DLPFC has been shown to alter impulsive choice behavior (to decrease delay discounting) in healthy individuals and in smokers (12). On the other hand, a trial of TMS by one of the leaders in the field has shown it to be safe and well tolerated in recent suicide attempters suffering from depression with comorbid post-traumatic stress disorder and traumatic brain injury (13).

UAMS investigators have used repetitive transcranial magnetic stimulation (rTMS) to understand and treat phantom sound perception in subjects with tinnitus and to examine risky choices and impulsive behaviors using delay discounting in smokers. We propose to replicate a randomized controlled trial of rTMS over 3 days in a sample of well characterized acutely suicidal inpatients.

Our overall hypothesis is that 10 Hertz rTMS of the left dorsolateral prefrontal cortex (DLPFC) will correct impulsive choice behavior deficits found in acutely suicidal patients that in turn will translate into faster resolution of acute suicidal ideation. The current proposal will expand our understanding of the neurobiology of suicidal behavior by examining a potential neurocognitive mechanism of acute suicidality and test the value of rTMS as intervention for acute suicidal behavior. The current proposal will utilize behavioral assessments and rTMS in a randomized controlled trial in a group of adult patients hospitalized: a) following a recent suicide attempt with persistent suicidal ideation, or b) for severe suicidal ideation (n=20). To meet this goal we plan to recruit up to 28 individuals. Specifically, we propose:

The primary objective/endpoint of this study is safety. Adverse events will be collected throughout the duration of the trial. Any subject that meets the criteria for withdrawal (*Safety Assessments, page 14*) will be withdrawn from the study. The study will be stopped and all subjects withdrawn if two completed suicides by subjects receiving TMS occur during the active TMS treatment.

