SA1. Determine the safety of repetitive transcranial magnetic stimulation (rTMS) in depressed patients with severe suicidal ideation.

Hypothesis 1: Given studies of rTMS for clinical depression, we predict that rTMS in patients with severe suicidal ideation will be well tolerated and not associated with significant side effects.

SA2. Determine the effect of rTMS on delay discounting on depressed patients with severe suicidal ideation.

Hypothesis 2: In depressed patients with severe suicidal ideation the rTMS active will reduce impulsive choice behavior (measured as delay discounting) compared with the non-treatment group

SA3. Determine the effect of rTMS on suicidal ideation on depressed patients with severe suicidal ideation.

Hypothesis 3.1: In depressed patients who had recently attempt suicide the rTMS active group will reduce suicidal ideation severity (measured by the Beck Scale for Suicidal Ideation) compared with the non-treatment group

Hypothesis 3.2: Suicidal ideation in depressed patients who recently attempt suicide will vary in function of

PI: [name] delay discounting.

SA4. Identification of biomarkers of positive response to rTMS in depressed patients with severe suicidal ideation.

Hypothesis 4: A composite of serum hormonal and inflammatory markers will predict positive response to rTMS in depressed patients with severe suicidal ideation.

Significance

Achieving the goals of this proposal will provide understanding of the neurobiological mechanisms of suicidality and proof of concept for the use of rTMS as adjunctive treatment for acute suicidality. This new knowledge would lead prospective studies testing the clinical value of rTMS to improve impulsive choice behavior to reduce suicide behavior in persons at high risk.

STUDY DESIGN AND PROCEDURES

Experimental design

A double blinded randomized controlled trial with assignment to active rTMS experimental treatments or sham will recruit adult patients (18-60 years old) of both genders voluntarily admitted to the PRI inpatient units following a recent suicide attempt with persistent suicidal ideation or because of severe suicidal ideation.

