The Principal Investigator will carefully monitor study procedures to protect the safety of research subjects, the quality of the data and the integrity of the study. To protect the identity of research volunteers, contact information will be stored in a separate file and locked cabinet, away from experimental data forms. All study subject material will be assigned a unique identifying code or number. The key to the code will be kept in a locked file in the Study Coordinator's office. Only [name] and designated research staff will have access to the code and information that identifies the subject in this study. All experimental data will be identified using a study code rather than a name, social security number, or other identifying information. All data collection forms will be kept in a locked cabinet in the Psychiatric Research Institute. Computer data records will remain on UAMS maintained password protected network drives.

DATA ANALYSIS

Cognitive tests and questionnaires

Data will be scored and analyzed/summarized according to instructions. Scores will be analyzed via t-tests, analysis of variance (ANOVA) or regression analysis.

PI: [name]

The primary outcome (impulsive choice measured by delay discounting) will be analyzed using an MMRM (mixed model repeated measures) approach based on a modified intent-to-treat (mITT) population. The mITT population will be defined as randomized subjects who started at least one treatment. Participants from the mITT population who are included in the MMRM model will also require both a baseline and at least one post- baseline SSI score. The model will include as the dependent variable change from baseline in delay discounting indifference point (K) at each post-baseline visit during the acute phase. Independent variables in the MMRM model will include treatment, visit, treatment-by-visit interaction, delay discounting at baseline, gender, age at baseline and diagnosis. Visits (Days 0, 1, 2, 3) will be treated as a categorical variable. Unstructured variance-covariance structure will be used. This same analysis will also be repeated on the completers' population, defined as subjects who completed 3 days of treatment with the scheduled maximum 6000 pulses per session.

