Analyses of VAS data will be conducted using a similar MMRM approach. Each VAS item will be analyzed separately. For the suicide, mood and anxiety items, the model included as the dependent variable change scores from pre-session 1 (session prior to intervention) to each post-session (sessions 1-9) during the acute phase. Independent variables included treatment, session, treatment-by-session interaction, VAS score at pre-session 1, gender, age at baseline, and diagnosis. Painfulness questions collected only at each post-session will be analyzed using an MMRM approach with post-session scores as the dependent variable. Independent variables will remain the same.

Descriptive analyses will be performed to compare baseline data between treatment groups. Categorical variables will be evaluated using Fisher's exact test. Continuous variables will be analyzed with Wilcoxon's rank sum test.

Safety data will be summarized overall and by treatment groups. Fisher's exact test will be used to compare the number of subjects between groups who experienced any adverse events. Length of hospital stay will be compared using Wilcoxon Rank Sum test. Time to re-admission will be analyzed with log-rank test.

The Stroop Test, N-Back scores and pain pressure threshold will be added as covariates in final analysis. Other secondary efficacy outcomes (HRSD, MADRS, CAPS and SSI) for the extended safety phase will be analyzed with MMRM model. The model will include the change from baseline at each follow-up visit as the dependent variable. Independent variables include treatment, visit, treatment-by-visit interaction and base- line score.

We will use repeated measures ANOVA (with appropriate statistical corrections) to compare measures obtained at baseline to those collected 3 & 6 months after all experimental treatment ends. This analysis will address long-term effects of rTMS experimental treatment on suicidal ideation.

The integrity of the blind will be analyzed by tables and Fisher's exact test.

All statistical analyses will be performed in R version 2.14.0. Because this is an early phase study, no adjustments will be made for multiple comparisons, and a *P*-value of 0.05 will be considered to be statistically significant.

Power estimation

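### Safety and delay discounting are both labelled primary without a stated ranking, and the only inference on adverse events is an any-event Fisher test with no confidence interval

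*Combined protocol and SAP*

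**What the plan says.** **Hierarchy.** The closing paragraph of Background and Rationale reads "The primary objective/endpoint of this study is safety". The aims follow in the same order: "SA1. Determine the safety of repetitive transcranial magnetic stimulation (rTMS) in depressed patients with severe suicidal ideation" and then "SA2. Determine the effect of rTMS on delay discounting on depressed patients with severe suicidal ideation". Data Analysis, under its subheading on cognitive tests and questionnaires, reads "The primary outcome (impulsive choice measured by delay discounting) will be analyzed using an MMRM". Later in that section comes "Other secondary efficacy outcomes (HRSD, MADRS, CAPS and SSI) for the extended safety phase will be analyzed with MMRM model". Nothing calls the two co-primary, ranks them, or describes delay discounting as the primary efficacy outcome.

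**Delay-discounting model.** "Independent variables in the MMRM model will include treatment, visit, treatment-by-visit interaction", together with baseline covariates. No contrast from the model is named as the main one.

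**Safety.** Hypothesis 1 predicts that "rTMS in patients with severe suicidal ideation will be well tolerated and not associated with significant side effects". It gives no rate, margin or threshold. Data Analysis plans summaries overall and by group, and a Fisher exact test on the number of subjects with any adverse event. Several related measures are analysed separately:
- Young Mania Rating Scale and D-KEFS scores, under the general provision for tests and questionnaires;
- each VAS item by MMRM (the items include discomfort and suicidality), plus painfulness ratings;
- length of stay by rank sum test and time to re-admission by log-rank test.

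Collection is thorough: MedDRA coding, withdrawal criteria, grading of relatedness, seriousness and severity, and a monitoring board. No confidence interval is planned anywhere, and no analysis set is named for the safety tables.

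**The concern.** The first sentence quoted says endpoint as well as objective, so the clash is not resolved by treating safety as an objective and delay discounting as an outcome. If the hierarchy is left to inference, the report can lead with whichever result reads better: tolerability if delay discounting is null, or delay discounting if it is not.

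For the safety aim, the question is what the trial will be able to say at the end. Hypothesis 1 predicts an absence of significant side effects. A test of no difference in a very small sample will usually be non-significant whether or not there is an excess, and a p-value does not show which event rates the data have ruled out. The any-event count also puts scalp discomfort and a seizure in the same yes/no category.

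**Working it through.** **No planned figure to reproduce.** The Power estimation section argues from the discounting rate K and names tinnitus as the outcome. No event rate, margin or precision target is given for adverse events, so the rates and counts below are assumptions or illustrations.

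**Inputs.** The target is 20 subjects randomised 1:1, giving 10 per arm; up to 28 may be recruited, giving 14 per arm if all are randomised evenly (both from Study Population). The significance level is 0.05 (Data Analysis). Sidedness is not stated; two-sided is assumed.

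**1. Smallest significant split.** With equal arms of n and all x events on one side, the two-sided Fisher p-value is 2 × C(n,x)/C(2n,x).
- 4/10 v 0/10: 2 × 210/4845 = 0.087
- 5/10 v 0/10: 2 × 252/15504 = 0.033
- 4/14 v 0/14: 2 × 1001/20475 = 0.098
- 5/14 v 0/14: 2 × 2002/98280 = 0.041

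Five events against none are needed at either size. One sham event raises the bar with 10 per arm: 6/10 v 1/10 gives 2 × (210×10 + 120)/77520 = 0.057, still not significant. If a one-sided test was meant, 4/10 v 0/10 would pass (210/4845 = 0.043).

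**2. Power of the any-event test.** Power is the sum of Bin(a; n, p1) × Bin(b; n, p2) over all pairs (a, b) with two-sided Fisher p ≤ 0.05.

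| Assumed rates, active v sham | 10 per arm | 14 per arm |
|---|---|---|
| 30% v 10% | 5.7% | 13.7% |
| 60% v 30% | 12.3% | 21.6% |
| 50% v 0% | 62.3% | 91.0% |

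With a true tripling from 10% to 30%, the test is non-significant in about 94% of trials with 10 per arm (100 − 5.7) and 86% with 14 (100 − 13.7).

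**3. What zero events rule out.** The two-sided exact 95% upper limit after 0/n is 1 − 0.025^(1/n).
- 0/10: 1 − 0.025^(1/10) = 30.8%
- 0/14: 1 − 0.025^(1/14) = 23.2%

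An event with a true rate of 10% would not appear at all in the active arm in 0.9^10 = 35% of trials with 10 active subjects, or 0.9^14 = 23% with 14.

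**4. What an interval would add.** Suppose 5/10 v 5/10, so the arms look identical. The Wilson limits for 5/10 are 0.237 and 0.763, each 0.263 from 0.5. The Newcombe 95% interval for the risk difference is 0 ± √(0.263² + 0.263²), or about −37 to +37 percentage points. The Fisher test reports only no difference; the interval shows that a large excess is still compatible with the data.

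**The case against.** **The hierarchy can be worked out.** The sentence on delay discounting sits under a subheading for cognitive tests and questionnaires, so it may mean only the lead outcome of that domain. The aim order and the reference to other secondary efficacy outcomes fit this. The point has force and makes the defect mild, perhaps one missing word. It does not settle the matter, because the safety tests appear under the same subheading.

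**Safety inference is wider than one test.** This is correct, and the point is limited accordingly: the mania scale, verbal fluency, VAS items, length of stay and re-admission are all analysed. The Fisher test is the only inference on adverse events as labelled, not on every safety-related measure.

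**The plan never equates p>0.05 with safety.** A reader might infer that it does, but nothing in the text says so. By-group summaries are planned, and anyone could compute intervals from them. What stands is that the plan offers no other inferential route from adverse events to Hypothesis 1.

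**A reader might infer that the Fisher test conceals harm.** For 4/10 v 0/10, p is 0.087 while the Newcombe interval is +4 to +69 points and excludes zero. This is small-sample disagreement between methods: the conditional exact odds-ratio interval that matches Fisher starts at 0.77 and includes 1. It shows why the interval method should be named in advance, and nothing stronger.

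**A reader might infer an inflated error rate from the open MMRM contrast.** Picking the best of Days 1, 2, 3 and their mean gives a 9% to 15% chance of at least one p<0.05 under no effect. That figure assumes deliberate picking, between-day correlations of 0.9 to 0.3, t-tests in place of the MMRM, and three visits where Table 2 schedules five post-baseline acute assessments. It is illustrative and is not this trial's error rate. The plan also openly declines multiplicity adjustment as an early-phase study.

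**Conclusion.** The point holds in two limited parts and should be fixed.

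First, two current passages give the primary label to different things and no passage ranks them. That rests on the text alone. The documents do not support reading this as two competing co-primary hypotheses; the likely intent is a primary safety objective plus a primary efficacy outcome, left unstated. The unnamed MMRM contrast is missing detail worth supplying, but the finding does not depend on it.

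Second, a non-significant any-event Fisher test at this size cannot support Hypothesis 1: power is about 6% (10 per arm) to 14% (14 per arm) for an assumed 30% v 10%, and zero active-arm events leave rates up to 31% or 23% compatible with the data. The power figures depend on assumed rates and a two-sided test; the upper limits depend only on the number of active subjects. Small size is acceptable in a pilot, but it is the reason to report the safety aim as estimates with intervals.

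**What to change.** 1. **Hierarchy.** Use the same wording in Background and Rationale and in Data Analysis, for example safety as the primary objective assessed by estimation and delay discounting as the primary efficacy outcome. Preferably name one MMRM contrast in advance; the choice is the sponsor's.
2. **Adverse events.** Keep the planned summaries and Fisher test. Add per-arm counts with exact 95% intervals, and risk differences with intervals by a method named in advance. Do this for any, serious and device-related events, and for seizure, syncope and mania/hypomania.
3. **Analysis set.** Base these tables on subjects who started treatment, in line with the existing definition: "The mITT population will be defined as randomized subjects who started at least one treatment". The adverse-event definition covers the whole time a subject is enrolled, so list events between enrolment and first treatment separately.
4. **Interpretation.** State that a non-significant Fisher test is not evidence of safety. A target rate or margin is optional in a pilot.

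The cost is wording in two sections and intervals computed on data already collected, with no new patients or visits. The downside is a more modest safety conclusion.

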Recruitment/Screening: The patient population will be recruited from the 30-bed inpatient units at the PRI at UAMS. At least one member of our research team will be present during each day's morning report held at 7:45 am. Generally, in our inpatient unit, as new patients are admitted daily, their cases, specifically the circumstances surrounding the hospital admission are reviewed during the morning report meeting. At this time, the unit's psychiatrist(s) will discuss patients admitted within the past 24 hours for a recent suicide attempt or suicidal ideation and will provide our research team member with the names of potential eligible cases.

Potential research subjects will have an initial psychiatric interview with the inpatient treatment team for purposes of diagnosis and developing a treatment plan, as per standard procedures of the inpatient psychiatric unit. During the clinical psychiatric interview, the clinical staff will have gathered information that would generally indicate whether patient would be a candidate for this study. The clinical staff member conducting the initial interview will ask appropriate patients for approval to be approached by research staff. After the completion of the initial psychiatric interview with the patient, our research team member (PI, research nurse or study coordinator) will approach the patient to invite him/her to participate in a brief (15 minutes) interview.

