Visual Analog Scale	Approx. 10 min	A custom developed Visual Analog Scale (VAS) questionnaire will be administered on a laptop computer pre and post each treatment session. Subjects are asked to rate their treatment experiences using the following descriptors: happy, irritable, angry, excited, confused, calm, sad, anxious, nervous, bored, relaxed, tired, distracted, discomfort, and suicidality (13) VAS scores are converted to a scaling of 0-99 points.		
Sham validating measure	Approx. 2 min	Subjects are asked two questions regarding their perception of receiving treatment or placebo.		
MINI International Neuropsychiatric Interview (MINI)	Approx. 30 min	Structured clinical interview for DSM-IV and ICD-10 psychiatric diagnoses. It is fully validated and is a more time-efficient alternative to the SCID.		
Young Mania Rating Scale	Approx. 10 min	Used to assess manic symptoms. The scale has 11 items and is based on the patient's subjective report of his or her clinical condition over the previous 48 hours.		
Delis-Kaplan Executive Function System (DKEFS) Verbal	Approx. 3 min	A verbal fluency test that measures spontaneous production of words belonging to the same category or beginning with some designated letter.		

C-SSSRS, HAM-D, HAM-A, MINI and other rating scales will be administered by a trained member of the research team.

Randomization

A predefined, computer-generated randomization sequence will assign participants in a 1:1 ratio to active vs. sham rTMS groups using a block size of 6. This sequence assignment will occur prior to the initiation of the study. Following completion of baseline assessments each subject will be assigned a sealed envelope with X or Y which will stand for active or sham stimulation.

The blind will be broken following completion of data gathering and analysis.

TMS

A NeuroStar TMS Therapy System and NeuroStar XPLOR Clinical Research System coil system (Neuronetics, Malvern Pennsylvania) will be used to deliver stimulation. The manuals for the stimulator and

PI: [name]

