Repetitive TMS (rTMS) will be delivered to the left PFC, defined as a location 6 cm (cm) anterior to the right hand motor thumb area. A research nurse will deliver the treatments. rTMS will be delivered with a figure-eight coil at 120% motor threshold, 10 Hertz (Hz), 5 s (s) train duration, 26 s intertrain interval for 50 min (6000 pulses) 3 times daily for 3 days (total 9 sessions, 54,000 stimuli). Similar parameters were previously used in a population of acutely suicidal veterans and military patients with even more severe comorbidity than our proposed sample because of comorbid posttraumatic stress disorder and traumatic brain injury without significant adverse effects (13). Variations will be allowed in the dosing schedule to accommodate the patient's inpatient schedule and staffing needs, with at least 1 hour between sessions. Treatments will be done on consecutive days, with the goal to deliver 9 sessions over three days. Adverse events will be assessed at each treatment session as well as daily. Prior to and then immediately after each rTMS session, subjects will complete visual analog scales (VAS) on a laptop computer located next to the rTMS chair. Patients will wear earplugs and will not be allowed to sleep. Counseling or other conversation during treatment will be discouraged.

Sham treatment

Parameters for sham rTMS are identical to those for active stimulation except that aluminum plate blocks the propagation of a magnetic field. The sound and physical sensation is the same as with the active coil while been biologically inactive.

Assessments

Trained and blinded study staff (raters) will administer assessments as described in Table 2. Additionally, menstrual cycle phase will be characterized for female subjects (i.e. date of last period, regularity of menstrual cycle).

PI: [name]

Table 2. Assessments administration schedule during the proposed study									
Task	Intake &	Pre rTMS	Post rTMS	Post	Before	3 & 6 month			
	Pre rTMS	Session 1	Session 3	rTMS	Discharge	follow-up			
	Session 1	(day 2 & 3)	(day 1 & 2)	Session 3					
	(day 1)			(day 3)					
Informed Consent Capacity	X								
Checklist									
Informed consent	X								
Demographic Data Form	X								
Columbia Suicide Severity Rating	X				X	X			
Scale (C- SSRS)									
Hamilton Rating Scale for	X			X	X	X			
Depression (HAM-D)									
Hamilton Anxiety Rating Scale	X			X	X	X			
(HAM-A)									
Beck Scale for Suicidal Ideation	X			X	X	X			
Beck Hopelessness Scale	X	X	X	X	X	X			

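### A single stated block size of 6 and one X/Y code for all subjects leave allocation concealment weak, because the research nurse role both recruits and treats

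*Combined protocol and SAP*

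**What the plan says.** All references are to the combined protocol and SAP.

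- **Randomization.** A computer-generated list will "assign participants in a 1:1 ratio to active vs. sham rTMS groups" "using a block size of 6". On timing: "This sequence assignment will occur prior to the initiation of the study". After baseline assessments, "each subject will be assigned a sealed envelope with X or Y which will stand for active or sham stimulation". On unblinding: "The blind will be broken following completion of data gathering and analysis".
- **Recruitment/Screening.** After the clinical interview, "our research team member (PI, research nurse or study coordinator) will approach the patient".
- **Active experimental treatment.** "A research nurse will deliver the treatments".
- **TMS.** The active and sham coils look alike and carry no label.
- **Sham treatment and Assessments.** Sham is described as matching active stimulation in sound and feel, and raters are blinded.
- **Study Population.** The target is 20 randomized; 28 are to be recruited.

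The document does not say who prepares, holds or opens the envelopes, or whether they are opaque and numbered in sequence. It does not say whether the block size is withheld from recruiting staff, or how one subject could be unblinded without decoding the others.

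**The concern.** Two features weaken concealment, and each makes the other worse.

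1. **One known block size.** In blocks of 6 with three of each letter, the letters already used in a block say something about the next one, and sometimes fix it. Because the coils carry no label, someone must use the letter, or an equivalent, to choose the coil. That is an inference from the text. No separate operator is named, and the treating role is also a recruiting role.
2. **One code for all subjects.** X means the same thing for every patient, so learning one patient's arm gives the meaning of both letters.

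The document itself describes events that could reveal an arm. Under the rare TMS risks, the PI would document that a seizure was caused by rTMS. The stopping rule counts suicides among subjects receiving TMS. The physician or nurse also watches for hand-muscle twitching during and after sessions, although how often this would give the arm away is not stated.

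At stake is who is approached, and when, in a trial of about 10 per arm, where one patient is 10% of an arm. Blinding of treating staff is also at stake. The planned check of the blind asks only patients, so it would not detect an operator who had worked out the code.

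**Working it through.** The document gives no figure for predictability, so there is none to reproduce.

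**Inputs.** Ratio 1:1 and block size 6 (Randomization); 20 to 28 subjects (Study Population). Assumption: the observer has seen all earlier letters and knows where blocks begin.

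**One block.** There are C(6,3) = 20 equally likely orders of 3 X and 3 Y.

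The next letter is certain when one letter has been used up:
- Positions 1 to 3: never.
- Position 4: the first three are all alike, 2/20 = 0.10.
- Position 5: one letter fills three of the first four places, (4 + 4)/20 = 0.40.
- Position 6: always, 1.00.
- Sum: 0.10 + 0.40 + 1.00 = 1.5 of 6 (25%).

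Guessing the letter used less often so far, with a coin toss when tied, is right with these probabilities by position: 0.5, 0.6, 0.6, 0.7, 0.7, 1.0. The sum is 4.1 of 6 (68%).

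**Whole trial.** Neither 20 nor 28 is a multiple of 6, so the last block is incomplete.

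| Subjects | Certain | Guessed correctly |
|---|---|---|
| 20 = 3 blocks + 2 | 3 × 1.5 + 0 = 4.5 (22.5%) | 3 × 4.1 + 0.5 + 0.6 = 13.4 (67%) |
| 28 = 4 blocks + 4 | 4 × 1.5 + 0.1 = 6.1 (21.8%) | 4 × 4.1 + 0.5 + 0.6 + 0.6 + 0.7 = 18.8 (67%) |

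If no letters are seen, the hit rate is 50%.

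**Varying block sizes.** These are simulated lists with sizes equally likely and an observer who knows the set of sizes but not the order. Ranges cover 20 and 28 subjects.

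| Block sizes | Certain | Best-guess hit rate |
|---|---|---|
| 6 only | about 22% | about 67% |
| 4, 6 | about 6% | about 69% |
| 4, 6, 8 | about 2% | about 67% |
| 2, 4, 6 | about 4% | about 70% |

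Varying the sizes removes most of the certainty but not the guessing advantage. The guessing rule uses only the running imbalance, which returns to zero at the end of every block whatever its size. Small blocks raise the hit rate: a block of 2 alone gives (0.5 + 1.0)/2 = 75%. This is why size 2 should be left out.

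**Reach of one disclosure.** With a constant X/Y, a person who learns one arm decodes every patient whose letter he or she knows, and predicted letters become predicted arms. With a unique code per subject, the same event discloses 1 of 20 (5%), and there is no repeated letter to count.

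**The case against.** Fixed permuted blocks, a computer-generated list and sealed envelopes are a recognised method, and this is a 20-patient pilot whose stated primary objective is safety. Unit psychiatrists name the candidates, clinical staff ask permission first, and the envelope comes after consent and baseline assessments. No text says that the nurse opens envelopes. A predicted letter gives bias no direction until its meaning is known.

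Much of this stands. It makes the figures upper bounds and keeps the point moderate. It does not remove the point: a prediction built from earlier letters exists before the next envelope is assigned, and the document describes nothing that keeps those letters from the recruiting roles.

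A reader might infer more than the document supports:
- **That one unblinding exposes all 20 to 28 patients.** It exposes those whose letter is known to the person who learns the code.
- **That a broken code removes the blind for rated and self-reported outcomes.** Raters are blinded and the sham is described as matching in sound and feel. A nurse who learns the code does not by that alone unblind raters or patients.
- **That the block size was public during enrolment.** It is written in the protocol; the registration section promises only a description of the trial.
- **That one individual recruits and treats.** The text shows a shared role, not a shared person.

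**Conclusion.** The concern holds as a weakness in allocation concealment and in containing a disclosure. For an observer who has seen all earlier letters and tracks the blocks, about 22% of assignments are certain and about 67% can be guessed, against 50% by chance. One known arm decodes every patient whose letter that observer knows. The stated safeguards address assessment bias, not these two matters.

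The finding rests on the inference that someone close to treatment uses the letter to choose the coil, and on the absence of any stated separation between that person and recruitment. It does not show that assignments were predicted or patients selected. The constant code is the more important half, because varying the blocks leaves the guessing advantage in place. The change is worth making because it costs little.

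**What to change.** Before enrolment:

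1. Regenerate the list with randomly varying block sizes that omit 2, for example 4, 6 and 8.
2. Remove the sizes from the protocol text that staff use.
3. Have the list held by existing staff outside recruitment and treatment, and say so in the Randomization section.
4. Where the coil hardware allows it without extra staff, replace the constant X/Y with subject-specific codes, or several codes per arm, so that one disclosure reveals one or a few patients.

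Steps 1 to 3 cut certain assignments from about 22% to about 2% (about 6% with sizes 4 and 6), but the best-guess rate stays near 67 to 69% for anyone who still sees the letters. Only step 4 limits how far one disclosure reaches. If the hardware permits only two labels, steps 1 to 3 are still worth doing for the loss of certainty.

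The cost is a new list, new envelopes and some relabelling. With blocks of 8, the arms can differ by at most 4 within a block, instead of 3 with blocks of 6.
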